6.1.1. General Considerations for the Open-Label Treatment Period (Period 2)

Baseline will be defined as the last available value on or prior to the first injection of the study drug for both efficacy, health outcomes, and safety analyses. In most cases, this will be the measurement recorded at Week 0 (Visit 2).

Categorical and continuous data will be summarized as described in Section 6.1.

Comparisons of ixekizumab versus adalimumab will be performed for all outcome variables in Period 2, as deemed appropriate, using methods described in Section 6.2.

Safety will be assessed by summarizing and analyzing adverse events (AEs), laboratory analytes including neutrophil counts, vital signs, and concomitant medications. The duration of exposure will also be summarized.

6.1.2. General Considerations for the Post-Treatment Follow-Up Period (Period 3)

Unless otherwise specified, the baseline for the safety analyses in Period 3 is defined as the last nonmissing assessment on or prior to entering Period 3, that is on or prior to Week 52 (Visit 11) or ETV.

The categorical safety measures will be summarized with incidence rates. The mean change of the continuous safety measures will be summarized by visits.

6.1.3. Analysis Populations

The follow analysis populations will be used:

Intent to Treat Population (ITT): The ITT Population consists of all randomized patients. Even if the patient does not take the assigned treatment, does not receive the correct treatment, does not receive any medication, or otherwise does not follow the protocol, the patients will be analyzed according to the treatment to which they were assigned at Week 0. Unless otherwise specified, all efficacy and health outcomes analyses for the Open-Label Treatment Period (Period 2) will be conducted on the ITT population.

Safety Population: The Safety Population is defined as all randomized patients who received at least 1 dose of study treatment. Patients will be analyzed according to the treatment to which they were assigned at Week 0. Unless otherwise specified, all safety analyses for the Open-Label Treatment Period will be conducted on the Safety Population.

Post-Treatment Follow-Up Population: The Post-Treatment Follow-Up Population consists of all randomized patients who received at least 1 dose of study treatment during Period 2 and have entered the Post-Treatment Follow-Up Period. Safety analyses for Period 3 (Post-Treatment Follow-Up Period) will be conducted on this population. Patients will be analyzed according to the last treatment they received before entering Period 3 (see treatment groups defined in [Table RHCF.6.1](#)).

[Table RHCF.6.2](#) gives the description of each of the population sets in the study as well as their intended analysis purposes.

Table RHCF.6.2. Efficacy, Health Outcomes, and Safety Measures Summarized and/or Analyzed for Each Analysis Population

Population Name	Measurement Summarization of Population
All Patients Entered	Tables for patient allocation and analysis populations, patient disposition
Intent-to-Treat Population	Tables, listings and/or figures for the following: patient disposition, important protocol deviations, patient characteristics, historical diagnoses, pre-existing conditions, previous therapies, concomitant medications, primary and secondary efficacy measures, health outcomes, exploratory measures for the Open-Label Treatment Period (Period 2)
Safety Population	Tables, listings and/or figures for safety assessments, treatment compliance, duration of exposure for the Open-Label Treatment Period (Period 2)
Follow-Up Population	Tables, listings and/or figures for the following: patient disposition, concomitant medications, and safety assessments for the Post-Treatment Follow-Up Period (Period 3)

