10.2. Populations for Analyses

For purposes of analysis, the following populations are defined:

Population	Description				
Entered	All participants who sign informed consent				
Randomized	Participants who met all entry criteria and were assigned a study treatment				
Intent-to-treat (ITT)	The ITT population consists of all randomized patients. Even if the patients do not take the assigned treatment, do not receive the correct treatment, or otherwise do not follow the protocol, they will be analyzed according to the treatment group to which they were assigned. Unless otherwise specified, efficacy and health outcomes analyses for Period 2 will be conducted on the ITT population.				
Safety	The safety population consists of all randomized patients who received at least 1 dose of study treatment in Period 2. Patients will be analyzed according to the treatment group to which they were assigned. Safety analyses for Period 2 will be conducted on this analysis set.				
Post-treatment follow-up	The post-treatment follow-up population consists of all randomized patients who received at least 1 dose of study treatment during Period 2 and have entered the Post-Treatment Follow-Up Period. Patients will be analyzed according to the treatment group to which they were assigned in Period 2. Safety analyses for Period 3 (Post-Treatment Follow-Up Period) will be conducted on this analysis set.				

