Data collected at early termination visits will be mapped to the next planned visit number for that patient. For by-visit summaries, only visits in which a measure was scheduled to be collected will be summarized. Unplanned/unscheduled measurements will be excluded from the mixed-effects model of repeated measures (MMRM) analysis. However, the data will still be used in other analyses; such analyses include, but are not limited to, shift analyses and modified baseline observation carried forward (mBOCF) endpoint analyses.

All confidence intervals (CIs) and statistical tests will be 2-sided with an α level of 0.05 unless specified otherwise. P-values that are greater than or equal to 0.001, and less than or equal to 0.999, will be presented to 3 decimal places. All other p-values that are less than 0.001 will be presented as <0.001, while p-values greater than 0.999 will be presented as >0.999. Confidence intervals will be presented to 1 more decimal place than the raw data.

Age, sex, and race will be reported on all by-patient listings unless otherwise specified. Sex will be abbreviated as follows: female (F) and male (M). Race will be abbreviated as follows: American Indian or Alaska Native (AI), Asian (AS), Black or African American (BL), Native Hawaiian or other Pacific Islander (NH), White (WH), and Multiple (MU).

Table RHCF.6.1 gives the treatment groups to be displayed for each treatment period and analysis population. Analysis populations are defined in Section 6.1.3. Note: “IXE” and “ADA” will be included in treatment group names for ixekizumab and adalimumab, respectively, in the statistical reports where applicable.

Table RHCF.6.1. Treatment Groups for Each Treatment Period and Analysis Population

Treatment Period	Analysis Population	Treatment Groups	Abbreviation	Comparison
Open-Label Treatment Period (Period 2)	Intent-to-Treat Population; Safety Population	Ixekizumab 80 mg Q4W (or Q2W/Q4W) Adalimumab 40 mg Q2W	IXE ADA	IXE vs ADA
Post-Treatment Follow-up Period (Period 3) ^a	Follow-up Population	Ixekizumab 80 mg Q4W (or Q2W/Q4W) Adalimumab 40 mg Q2W	IXE ADA	Not applicable

Abbreviations = ADA = adalimumab; IXE = ixekizumab; Q2W = every 2 weeks; Q4W = every 4 weeks.

^a Treatment group refers to the dosage regimen that the patient received immediately prior to entering the Post-Treatment Follow-up Period.

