6.15.3. Deaths, Other Serious Adverse Events, and Other Notable Adverse Events

By-patient listings of deaths, SAEs, and AEs leading to discontinuation will be provided, respectively.

All deaths will be included, regardless of the investigator's or the sponsor's judgment about causality, including the following:

- any deaths occurring during participation in the study in the database for which data are being presented
- any deaths occurring after a patient leaves (is discontinued from or completed) the study in the database for which data are being presented if the death is:
 - the result of a process initiated during the study, regardless of when it actually occurred, or
 - occurs during Period 3 after discontinuation of study drug

An SAE is any AE that results in one of the following outcomes: death; life-threatening, initial, or prolonged hospitalization; disability or permanent damage; congenital anomaly or birth defect; or any other serious/important medical events.

The following summary tables (including treatment group comparison for Period 2) will be provided for the Safety Population during the Open-Label Treatment Period (Period 2):

- SAEs by SOC and PT
- AEs that lead to treatment discontinuation (including death) by SOC and PT

The following summary tables (by treatment group during Period 2) will be provided for the Post-Treatment Follow-Up Population during the Post-Treatment Follow-Up Period (Period 3):

- Follow-up emergent SAEs (FESAEs) by SOC and PT
- FEAEs that lead to treatment discontinuation (including death) by SOC and PT

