Had unqualified site personnel perform clinical safety and/or efficacy assessments	Monitor	Monitor's list
Unblinding of the blinded rater at the site	Monitor	Monitor's list

Category: Investigational Product		
Sub-Category: Treatment Assignment/Randomization Error		
Took incorrect study medication	Monitor and Stats	Monitor's list; or If IWRS study drug dispense data not match with the treatment label identifier on the Exposure as Collected eCRF page
Sub-Category: Compliance	Monitor and Stats	Monitor's list; or If non-compliant with study medication regimen or over-dose during the treatment period. Note: Non-compliance with therapy is defined to be missing more than 20% of expected doses and missing 2 or more consecutive doses; over-dose is defined as to take more injections at the same time point than specified in the protocol.
Sub-Category: Patient took medication not fit for use	Monitor	Monitor's list
Sub-Category: Other		
Randomized but did not take any study medication	Monitor	Monitor's list
Sub-Category: Treatment Assignment /Randomization Error		
Stratification error leading to incorrect dosing regimen	Monitor and Stats	Monitor's list; or If IWRS stratification data does not match patients' severity of plaque psoriasis (PASI, sPGA and BSA)

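### Safety data are grouped by assigned drug in Period 2 and by last treatment received in Period 3; the protocol and SAP passages conflict and need one rule

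*SAP*

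**What the plan says.** **Period 2.** SAP 6.1.3 applies one rule to both the ITT and the Safety Populations: "patients will be analyzed according to the treatment to which they were assigned at Week 0". Protocol 10.2 agrees: its safety population is also grouped by assignment.

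**Period 3.** SAP 6.1.3 changes the rule for the Post-Treatment Follow-Up Population: "Patients will be analyzed according to the last treatment they received before entering Period 3". The footnote to SAP Table RHCF.6.1 repeats it: "Treatment group refers to the dosage regimen that the patient received immediately prior to entering the Post-Treatment Follow-up Period". Protocol 10.2 keeps assignment: "Patients will be analyzed according to the treatment group to which they were assigned in Period 2". SAP 6.15.3 introduces the Period 3 tables of serious events and of events leading to discontinuation this way: "The following summary tables (by treatment group during Period 2) will be provided for the Post-Treatment Follow-Up Population".

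**Wrong-drug cases.** SAP Table RHCF.6.9 lists "Took incorrect study medication" as an important protocol violation. It can come from the monitor's list or from a programmed check that begins "If IWRS study drug dispense data not match with the treatment label identifier on the" and refers to the exposure page of the case report form. Neither document plans a safety analysis by drug actually received.

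**The concern.** A safety table by arm is read as a statement about what each drug did. If a patient took the other drug, the as-assigned rule credits that patient's on-treatment events to the assigned drug. Exposure is affected too: SAP 6.15.1 sums the dose of the injections taken and summarises it by treatment group, so milligrams of one drug would enter the other drug's total. Mixing drugs across arms tends to pull the arms together, which is not the cautious direction for harm.

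The Period 3 wording adds a second problem. Four passages describe the grouping and do not agree, so a programmer with a wrong-drug patient cannot satisfy all of them. The two periods are also linked: under SAP 6.15.2.1, an event already counted as treatment-emergent is not counted again as follow-up emergent. One patient's history could therefore be split between two arms.

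**Working it through.** The plan states no figure on this point. The check compares the passages and then gauges the size.

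**Step 1. Passages side by side.**

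| Passage | Period 2 safety | Period 3 safety |
|---|---|---|
| Protocol 10.2 | assigned | assigned |
| SAP 6.1.3 | assigned | last treatment received |
| SAP Table RHCF.6.1, footnote | not addressed | regimen received just before Period 3 |
| SAP 6.15.3 (serious and discontinuation events) | not addressed | Period 2 treatment group |

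The two documents agree on Period 2 and disagree on Period 3. The SAP revision history covers changes since Version 1, lists none to 6.1.3, and so gives no reason for the departure.

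**Step 2. Follow a patient assigned drug A who receives drug B.**

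- *B from the first dose to the last.* Period 2 events and exposure count under A. Period 3 events count under B by SAP 6.1.3 and under A by protocol 10.2. SAP 6.15.3 most naturally gives A.
- *One wrong kit of B, then back to A.* Events during the wrong dose count under A. Period 3 is also A under every passage, so there is no change of arm.
- *A first, then B through the last dose.* Period 2 counts under A, including events after the switch. Period 3 counts under B by SAP 6.1.3.

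**Step 3. Dilution of the Period 2 risk difference.** Inputs: 275 per arm (SAP 5.2) and k patients who take the other drug throughout. The documents do not give k, so the values below are assumptions. If k patients in one arm are affected, that arm's expected risk is [(275 − k)·pA + k·pB]/275, and the difference is multiplied by 1 − k/275. If k in each arm are affected, the factor is 1 − 2k/275.

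| k (assumed) | k/275 | one arm affected | both arms affected |
|---|---|---|---|
| 1 | 0.4% | 0.996 | 0.993 |
| 5 | 1.8% | 0.982 | 0.964 |
| 14 | 5.1% | 0.949 | 0.898 |
| 28 | 10.2% | 0.898 | 0.796 |

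The last two rows only bound the range; nothing in the documents suggests rates that high.

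**Step 4. One rare event.** SAP 6.15 compares Period 2 adverse events with Fisher's exact test. Suppose one patient assigned to the first arm took the second arm's drug and had the event. By drug received the denominators are 276 and 274; by assignment they are 275 and 275. The event counts are illustrative.

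| By drug received | p | By assignment | p |
|---|---|---|---|
| 6/276 vs 0/274 | 0.030 | 5/275 vs 1/275 | 0.216 |
| 3/276 vs 0/274 | 0.249 | 2/275 vs 1/275 | 1.000 |
| 1/276 vs 0/274 | 1.000 | 0/275 vs 1/275 | 1.000 |

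Holding the denominators at 275 gives the same p-values to three decimals. Only a table that is both sparse and lopsided shows a visible change.

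**The case against.** The case for leaving the plan alone has several parts.

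- *Wrong-drug cases should be very rare.* Site staff enter a confirmation number from the product into the IWRS, treatment is open-label, and the two drugs have different schedules. Sustained use of the wrong drug is unlikely. This stands, and it limits the size of the point.
- *As-assigned grouping in Period 2 was prespecified in both documents.* This stands: for Period 2 the issue is the choice of rule, not a contradiction.
- *Period 3 carries no comparison.* Table RHCF.6.1 gives it as not applicable, and SAP 6.15 calls even Period 2 safety p-values descriptive. This stands.
- *The Table RHCF.6.1 footnote speaks of a regimen, and the table lists the same two groups for both periods.* The Period 3 rule could be read as carrying the Period 2 group forward. That reading is possible, but SAP 6.1.3 says last treatment received in plain words. The ambiguity is itself a reason to settle the text.

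Three stronger readings are tempting, and the documents do not support them.

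- *Every wrong-drug patient changes arm.* Only a patient whose last drug was the non-assigned one does.
- *The period split distorts MACE, inflammatory bowel disease and malignancy.* Table RHCF.6.7 plans those analyses for Period 2 only, so they are exposed to the as-assigned rule and not to the split.
- *Period 2 and Period 3 counts cannot be reconciled.* The follow-up population includes only patients who entered Period 3, so its counts need not match the Safety Population under any rule. By-patient listings of important deviations (SAP 6.17) and of deaths, serious events and discontinuation events (SAP 6.15.3) would let a reader trace the few cases.

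The mismatch check also does not prove which drug was taken. A mismatch could be another kit of the same drug, so each flagged case needs review.

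**Conclusion.** The point holds as a minor one. The Period 3 grouping rule differs between protocol 10.2 and SAP 6.1.3, and SAP 6.15.3 does not sit clearly with SAP 6.1.3. That is a textual conflict however many patients are affected. Separately, in Period 2 both documents count a wrong-drug patient's events and exposure under the assigned drug.

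The numerical effect is probably very small: 0.36% of an arm per patient, and a risk difference reduced by less than 4% even with five such patients in each arm (factor 0.964). It could matter for a single sparse table, as the change from p = 0.030 to p = 0.216 illustrates. These sizes rest on assumed numbers of wrong-drug patients and assumed event counts. ITT efficacy is not affected. The point concerns analysis grouping only, not clinical management.

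**What to change.** Use one rule for both periods. In SAP 6.1.3, group the Safety and Post-Treatment Follow-Up Populations by the drug actually received. State a rule for patients who received both drugs, for example the first drug received, plus a listing of events that occurred after a wrong dose. No single-arm rule places every event correctly for such patients, so the listing is needed.

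Keep assignment for ITT efficacy. If any wrong-drug case occurs, add an as-assigned sensitivity table. Bring protocol 10.2, SAP 6.1.3, the Table RHCF.6.1 footnote and SAP 6.15.3 into line, and record the change in the SAP revision history. If the team prefers to keep assignment for safety, the Period 3 wording still has to be reconciled.

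The cost is a few sentences of text and, where a case is flagged, a review of which drug was taken. No new data collection is needed. Safety and ITT denominators by arm may then differ by the few wrong-drug patients, which a table footnote can explain.

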6.2. Analysis Methods

6.2.1. Categorical

Unless specified otherwise, the primary analysis method for the binary categorical efficacy and health outcome variables will be a logistic regression model with treatment, concomitant csDMARD use at baseline, and moderate-to-severe plaque psoriasis involvement as factors. The odds ratios and the corresponding 95% CIs will be reported. Fisher's exact test will be used as the secondary analysis method.

For ordinal categorical variables, a logistic regression model using cumulative logits will be used.

Treatment differences (Absolute Risk Reductions [ARR]), Relative Risks (RR), Numbers Needed to Treat (NNT) estimates, and their corresponding 95% CIs (using normal approximation) will also be reported. See [Appendix 1](#) for more details.

The statistical methodology for assessing noninferiority of ixekizumab to adalimumab for ACR50 is described in [Section 6.7](#).

6.2.2. Continuous Endpoints

Unless specified otherwise, the primary analysis method for all continuous efficacy and health outcome variables will be a MMRM analysis. The model will include treatment group, concomitant csDMARD use at baseline, moderate-to-severe plaque psoriasis involvement, visit-as-fixed factors, baseline value as covariate and baseline-by-visit and treatment-by-visit interaction terms. The MMRM analyses will be conducted using a restricted maximum likelihood (REML)-based repeated measures approach. The covariance structure to model the within-patient errors will be unstructured. If the unstructured covariance matrix results in a lack

of convergence, the heterogeneous Toeplitz covariance structure, followed by the heterogeneous autoregressive covariance structure, followed by the compound symmetry structure will be used. The first structure to yield convergence will be used for inference. The Newton-Raphson with ridging optimization technique will be used to aid with convergence. The Kenward-Roger approximation will be used to estimate the denominator degrees of freedom and adjust standard errors. Type III tests for the least squares (LS)Means will be used for the statistical comparison; the 95% CI will also be reported.

An analysis of covariance (ANCOVA) model and mBOCF imputation method as detailed in Section 6.4.2 will be used as the secondary analysis method for treatment comparisons on continuous efficacy and health outcome variables. The ANCOVA model will include treatment, concomitant csDMARD use at baseline, moderate-to-severe plaque psoriasis involvement, and baseline value in the model. Type III sums of squares for the LSMeans will be used for the statistical comparison; the 95% CI will be reported.

6.3. Adjustments for Covariates

The randomization at the beginning of Open-Label Treatment Period (Period 2) is stratified by concomitant csDMARD use at baseline (Yes, No) and moderate-to-severe plaque psoriasis involvement (Yes, No). Unless otherwise specified, all efficacy and health outcome analyses during Period 2 will include the concomitant csDMARD use at baseline and moderate-to-severe plaque psoriasis involvement in the model. In general, when an MMRM is to be used for analyses, baseline value and baseline-by-visit interactions will be included as covariates; when an ANCOVA is to be used for analyses, baseline value will be included as a covariate.

The OBSMARGINS/OM option will be used in the LSMEANS statement in SAS to account for imbalance in the stratification variables.

6.4. Handling of Dropouts or Missing Data

6.4.1. Non-Responder Imputation (NRI) for Clinical Response

Analysis of categorical efficacy and health outcome variables will be based on treatment success/failure. This approach yields results numerically identical to non-responder imputation (NRI), but it is interpreted differently. Patients will be considered treatment failures (or non-responders) if they do not meet the clinical response criteria or have missing clinical response data at a particular time point of analysis.

6.4.2. Modified Baseline Observation Carried Forward (mBOCF)

Missing data for continuous efficacy and health outcomes variables will be imputed using a mBOCF method. For patients discontinuing investigational product due to an AE, including death, the baseline observation will be carried forward to the corresponding primary endpoint for evaluation. For patients discontinuing investigational product for any other reason, the last non-missing post-baseline observation before discontinuation will be carried forward to the corresponding time point of evaluation. Randomized patients without at least 1 post-baseline

observation will not be included for evaluation with the exception of patients discontinuing study treatment due to an AE (including death).

